Appendix 12.2 Definition of SAE

An SAE is defined as any adverse event that, at any dose:

a) Results in death

b) Is life-threatening

The term “life-threatening” in the definition of “serious” refers to an event in which the participant was at risk of death at the time of the event. It does not refer to an event, which hypothetically might have caused death, if it were more severe.

c) Requires inpatient hospitalization or prolongation of existing hospitalization

In general, hospitalization signifies that the participant has been admitted (usually involving at least an overnight stay) at the hospital or emergency ward for observation and/or treatment that would not have been appropriate in the physician’s office or outpatient setting. Complications that occur during hospitalization are AEs. If a complication prolongs hospitalization or fulfills any other serious criteria, the event is serious. When in doubt as to whether “hospitalization” occurred or was necessary, the AE should be considered serious.

Hospitalization for elective treatment of a pre-existing condition that did not worsen from baseline is not considered an AE.

d) Results in persistent or significant disability/incapacity

- The term disability means a substantial disruption of a person’s ability to conduct normal life functions.
- This definition is not intended to include experiences of relatively minor medical significance such as uncomplicated headache, nausea, vomiting, diarrhea, influenza, and accidental trauma (eg, sprained ankle) which may interfere with or prevent everyday life functions but do not constitute a substantial disruption.

e) Is a congenital anomaly/birth defect

f) Other situations:

- Medical or scientific judgment should be exercised by the Investigator in deciding whether SAE reporting is appropriate in other situations such as significant medical events that may jeopardize the participant or may require medical or surgical intervention to prevent one of the other outcomes listed in the above definition. These events should usually be considered serious.
- Note: The following list of medically important events is intended to serve as a guideline for determining which condition has to be considered as a medically important event. The list is not intended to be exhaustive:
 - Intensive treatment in an emergency room or at home for:
 - Allergic bronchospasm
 - Blood dyscrasias (ie, agranulocytosis, aplastic anemia, bone marrow aplasia, myelodysplasia, pancytopenia, etc)

- Convulsions (seizures, epilepsy, epileptic fit, absence, etc).
- Development of drug dependence or drug abuse
- ALT $>3 \times$ ULN + total bilirubin $>2 \times$ ULN or asymptomatic ALT increase $>10 \times$ ULN
- Suicide attempt or any event suggestive of suicidality
- Syncope, loss of consciousness (except if documented as a consequence of blood sampling)
- Bullous cutaneous eruptions

Appendix 12.3 Recording and follow-up of AE and/or SAE

AE and SAE recording

- When an AE/SAE occurs, it is the responsibility of the Investigator to review all documentation (eg, hospital progress notes, laboratory reports, and diagnostics reports) related to the event.
- The Investigator will then record all relevant AE/SAE information.
- It is **not** acceptable for the Investigator to send photocopies of the participant's medical records to the Sponsor's representative in lieu of completion of the required form.
- There may be instances when copies of medical records for certain cases are requested by the Sponsor's representative. In this case, all participant identifiers, with the exception of the participant number, will be redacted on the copies of the medical records before submission to the Sponsor's representative.
- The Investigator will attempt to establish a diagnosis of the event based on signs, symptoms, and/or other clinical information. Whenever possible, the diagnosis (not the individual signs/symptoms) will be documented as the AE/SAE.

Assessment of intensity

The NCI-CTCAE Version 5.0 will be used to assess the severity of AEs/SAEs.

The Investigator will make an assessment of intensity for each AE and SAE reported during the study and assign it to 1 of the following categories:

- | | |
|----------|---|
| Grade 1: | Mild; asymptomatic or mild symptoms; clinical or diagnostic observations only; intervention not indicated. |
| Grade 2: | Moderate; minimal, local, or noninvasive intervention indicated; limiting age-appropriate instrumental activities of daily living. |
| Grade 3: | Severe or medically significant but not immediately life-threatening; hospitalization or prolongation of hospitalization indicated; disabling; limiting self-care activities of daily living. |
| Grade 4: | Life-threatening consequences; urgent intervention indicated: by definition also a SAE. |

Death will not be recorded as a Grade 5 severity - rather the underlying condition will be recorded, and its severity graded, with death regarded as an outcome.

An event is defined as “serious” when it meets at least 1 of the predefined outcomes as described in the definition of an SAE, NOT when it is rated as severe.

Assessment of causality

- The Investigator is obligated to assess the relationship between study intervention and each occurrence of each AE/SAE.
- A “reasonable possibility” of a relationship conveys that there are facts, evidence, and/or arguments to suggest a causal relationship, rather than that a relationship cannot be ruled out.
- The Investigator will use clinical judgment to determine the relationship.
- Alternative causes, such as underlying disease(s), concomitant therapy, and other risk factors, as well as the temporal relationship of the event to study intervention administration will be considered and investigated.
- The Investigator will also consult the Investigator’s Brochure (IB) and/or Product Information, for marketed products, in his/her assessment.
- For each AE/SAE, the Investigator **must** document in the medical notes that he/she has reviewed the AE/SAE and has provided an assessment of causality.
- There may be situations in which an SAE has occurred, and the Investigator has minimal information to include in the initial report to the Sponsor. However, **it is very important that the Investigator always make an assessment of causality for every event before the initial transmission of the SAE data to the Sponsor.**
- The Investigator may change his/her opinion of causality in light of follow-up information and send an SAE follow-up report with the updated causality assessment.
- The causality assessment is one of the criteria used when determining regulatory reporting requirements.

Follow-up of AEs and SAEs

- The Investigator is obligated to perform or arrange for the conduct of supplemental measurements and/or evaluations as medically indicated or as requested by the Sponsor’s representative to elucidate the nature and/or causality of the AE or SAE as fully as possible. This may include additional laboratory tests or investigations, histopathological examinations, or consultation with other health care professionals.
- If a participant dies during participation in the study or during a recognized follow-up period, the Investigator will provide the Sponsor with a copy of any post-mortem findings including histopathology.
- New or updated information will be recorded in the originally submitted documents.
- The Investigator will submit any updated SAE data to the Sponsor within 24 hours of receipt of the information.

Appendix 12.4 Reporting of SAEs

SAE reporting to the Sponsor via an electronic data collection tool

- The primary mechanism for reporting an SAE to the Sponsor's representative will be the electronic data collection tool.
- If the electronic system is unavailable, then the site will use the paper SAE data collection tool (see next section) to report the event within 24 hours.
- The site will enter the SAE data into the electronic system as soon as it becomes available.
- After the study is completed at a given site, the electronic data collection tool will be taken off-line to prevent the entry of new data or changes to existing data.
- If a site receives a report of a new SAE from a study participant or receives updated data on a previously reported SAE after the electronic data collection tool has been taken off-line, then the site can report this information on a paper SAE form (see next section) or to the Sponsor's representative by telephone.
- Contacts for SAE reporting can be found in the Investigator Study File.

SAE reporting to the Sponsor via paper data collection tool

- Facsimile transmission of the SAE paper data collection tool is the preferred method to transmit this information to the Sponsor's representative.
- In rare circumstances and in the absence of facsimile equipment, notification by telephone is acceptable with a copy of the SAE data collection tool sent by overnight mail or courier service.
- Initial notification via telephone does not replace the need for the Investigator to complete and sign the SAE data collection tool within the designated reporting time frames.
- Contacts for SAE reporting can be found in the Investigator Study File.

Appendix 13 Contraceptive and Barrier Guidance

Appendix 13.1 Definitions

A **woman is considered WOCBP** (fertile) from the time of menarche until becoming postmenopausal (see below) unless permanently sterile (see below).

- A postmenopausal state is defined as the period of time after a woman has experienced no menses for 12 consecutive months without an alternative medical cause.
- A high FSH level in the postmenopausal range must be used to confirm a postmenopausal state in women not using hormonal contraception or hormonal replacement therapy (HRT).

Females on HRT and whose menopausal status is in doubt will be required to use one of the non-estrogen hormonal highly effective contraception methods if they wish to continue their HRT during the study. Otherwise, they must discontinue HRT to allow confirmation of postmenopausal status before study enrollment.

Permanent sterilization methods include:

- Documented hysterectomy
- Documented bilateral salpingectomy
- Documented bilateral oophorectomy
- For individuals with permanent infertility due to an alternate medical cause other than the above, (eg, Mullerian agenesis, androgen insensitivity, gonadal dysgenesis), investigator discretion should be applied to determining study entry eligibility.

Note: Documentation can come from the site personnel's review of the participant's medical records, medical examination, or medical history interview.

If fertility is unclear (eg, amenorrhea in athletes) and a menstrual cycle cannot be confirmed before first administration of study intervention, additional evaluation should be considered.

Women in the following categories are considered WONCBP:

1. Any female with permanent infertility due to one of the following:
 - Documented hysterectomy
 - Documented bilateral salpingectomy
 - Documented bilateral oophorectomy
 - For individuals with permanent infertility due to an alternate medical cause other than the above, (eg, Mullerian agenesis, androgen insensitivity, gonadal dysgenesis), Investigator discretion should be applied to determining study entry.

2. Postmenopausal female

A postmenopausal state is defined as the period of time after a woman has experienced no menses for 12 consecutive months without an alternative medical cause.

- A high FSH level in the postmenopausal range may be used to confirm a postmenopausal state in women not using hormonal contraception or HRT.

- Females on HRT and whose menopausal status is in doubt must discontinue HRT to allow confirmation of postmenopausal status before study enrollment.

Note: Documentation can come from the site personnel's review of the participant's medical records, medical examination, or medical history interview.

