- b At the Week 13 visit review previous platelet counts for response during the first 12 weeks. If the participant met the criteria for response continue with the Week 13 visit assessments, the participant should continue in the blinded part. If the participant did not meet the criteria for response, complete the Week 25 visit assessments and the participant may start the open label period or discontinue from the study. Platelet response is defined as a) a platelet count of $\geq 50,000/\mu\text{L}$ OR a platelet count of between $\geq 30,000/\mu\text{L}$ and $< 50,000/\mu\text{L}$ and at least doubled from baseline at any time during the first 12 weeks and b) absence of rescue medication in the 4 weeks prior to the latest elevated platelet count that meets platelet response criteria.) Participants who receive rescue medication during the last 12 weeks also may join the open-label part or discontinue from the study. See [Figure 1](#) for decision tree for assessing response at Week 13 and for calculation of baseline platelet count.
- c For pediatric participants (see [Appendix 10.7](#) for EU [EEA countries] age ranges) height is recorded at Screening, Week 13, Week 25, Week 37, and Week 53. For participants aged 18 years and older height is recorded at Screening only.
- d Full physical examination at Screening, 4-week follow-up and early termination; abbreviated physical examination at all other visits. Medical history should include vaccine history. See [Appendix 10.6](#) for Italy-specific requirements.
- e ECG for pediatric participants (see [Appendix 10.7](#) for EU [EEA countries] age ranges) will be performed predose and 2 hours postdose (± 15 mins) at the Week 1 and Week 25 visits.
- f Urinalysis: pH, specific gravity, protein, glucose, ketones, bilirubin, blood, nitrites, urobilinogen, and leukocytes.
- g Participants enrolled with positive HBV core antibody test result and HBsAb titer ≥ 100 IU/L will have HBV DNA monitored monthly while on treatment and for 6 months after treatment has ended.
- h For women of childbearing potential only. Serum pregnancy test must be performed at Screening; a urine pregnancy test must be performed at all other study timepoints.
- i To confirm postmenopausal status for women who are not surgically sterile and of reproductive potential.
- j Historical lab results may be used for ABO and Rh Blood Type.

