4.1.1. Screening (Day -28 to Study Day-1 Predose)

- Informed consent
- Verify participant meets Inclusion/Exclusion criteria (use screening lab results for eligibility determination, with the exception of hemoglobin, which is to be rechecked prior to dosing on Day 1)
- Complete ITP-PAQ or ITP-KIT, EQ-5D-5L and PGIS-Fatigue/PGIS/PGIC patient QOL questionnaires
- Record concomitant medications
- Record height (cm)
- Record weight (kg)
- Conduct full physical examination and medical history
- Complete IBLs
- Capture vital signs (body temperature, respiratory rate, blood pressure, and pulse rate)
- Collect 12-lead single ECG
- Collect urine sample for urinalysis
- Collect hepatitis B virus (HBV), hepatitis C virus (HCV) and human immunodeficiency virus (HIV) blood samples
- Collect QuantiFERON-Tuberculosis (TB) blood sample
- Collect serum blood sample pregnancy test (women of childbearing potential)
- Collect follicle-stimulating hormone (FSH) blood sample (postmenopausal woman only)

- Collect ABO and Rh Blood Type blood sample (historical results may be used)
- Collect clinical laboratory blood samples:
 - Hematology (hemoglobin, hematocrit, red blood cells [RBCs], platelets, mean platelet volume, white blood cells [WBCs] with differentials [neutrophils, eosinophils, basophils, lymphocytes, and monocytes])
 - Serum chemistry (aspartate aminotransferase [AST], alanine aminotransferase [ALT], total, direct, and indirect bilirubin levels, alkaline phosphatase [ALP], albumin, creatinine, urea, total protein, sodium, chloride, calcium, phosphate, potassium, and glucose [random]); creatinine phosphokinase (CPK) and estimated glomerular filtration rate (eGFR) (See [Appendix 10](#) for country-specific requirements) to be performed at screening only
 - Coagulation (prothrombin time [PT]/international normalized ratio [INR], thrombin time, activated partial thromboplastin time [aPTT], fibrinogen level)
- Record AEs
- Perform SARS-CoV-2 molecular test (if COVID-19 testing is required per local guidelines to be determined for each site).
- For country-specific requirements please refer to [Appendix 10](#).

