7.2. Study Enrollment Procedures

Participants eligible for screening cannot commence enrollment study procedures until the informed consent process and form has been properly administered and signed. Screening tests are then administered, including blood tests sent for laboratory testing. Where the clinical significance of an abnormal screening test result (lab or any other tests) is considered uncertain, the test may be repeated once at least 7 days apart.

The Investigator or designee will enter data for each enrolled participant in the study electronic case report form (eCRF) and enter the corresponding participant ID number in the appropriate place on each participant's eCRF. A participant enrollment and Identification Code List must be maintained by the investigator or pharmacist, or designee.

Under no circumstances will participants who enroll in this study and complete treatment as specified be permitted to re-enroll in the study.

During the COVID-19 pandemic, the Sponsor will need to assess the feasibility of implementing a plan for participant access to study drug and any additional measures required to monitor participant safety on an ongoing basis. Please notify the Sponsor and your contract research organization (CRO) study monitor if your site suspends participant enrollment.

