7.9.6. Clinical Laboratory Tests

See [Table 1](#), [Table 2](#) and [Table 3](#) for laboratory test panels for chemistry, hematology, urinalysis and pregnancy testing. Laboratory safety tests may be performed at unscheduled time points, if deemed necessary by the Investigator. Screening laboratory safety tests may be repeated upon discussion with the Sponsor/Medical Monitor.

The Laboratory Manual will supply complete written instructions for collection, handling, processing, storage, and shipping of samples.

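### Appendix 13.1 makes a high FSH mandatory to confirm menopause in one list and optional in the other, so a woman with a below-range FSH can be classed either way

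*Protocol*

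**What the plan says.** Protocol Appendix 13.1 gives the same base definition of menopause in both of its lists: 12 consecutive months without menses and no alternative medical cause. It then adds an FSH rule to each list, for the same women.

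- WOCBP list: "A high FSH level in the postmenopausal range must be used to confirm a postmenopausal state in women not using hormonal contraception" (the sentence goes on to name HRT as well).
- WONCBP list, category 2: "A high FSH level in the postmenopausal range may be used to confirm a postmenopausal state in women not using hormonal contraception or HRT".

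Both are current text, not entries in the amendment history. The only other guidance in the appendix for a doubtful case is that, if fertility is unclear and "a menstrual cycle cannot be confirmed before first administration of study intervention, additional evaluation should be considered".

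The schedule treats FSH as a Screening test. Table 1 footnote i gives its purpose: "To confirm postmenopausal status for women who are not surgically sterile and of reproductive potential". Section 4.1.1 lists "Collect follicle-stimulating hormone (FSH) blood sample (postmenopausal woman only") among the Screening procedures and tells sites to "use screening lab results for eligibility determination".

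Inclusion criterion 6B takes its definition of WONCBP from Appendix 13. A WOCBP must use highly effective contraception until at least 4 weeks after the last dose. The pregnancy-test footnotes (Table 1 footnote h, Table 2 footnote e, Table 3 footnote d) confine testing to WOCBP.

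**The concern.** Two sites that each follow Appendix 13.1 can put the same woman in opposite classes. A site relying on the optional wording can drop the contraception requirement and the scheduled pregnancy tests. A site relying on the mandatory wording applies both. Appendix 13.2 allows that the study drug may affect ova for up to 4 weeks, and pregnancy is a stopping criterion in Section 7.5.1. That criterion works only if a pregnancy is detected, and scheduled testing is one of the means of detecting it.

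The stake is reproductive safety and uniform conduct across sites. It is not a statistical matter.

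**Working it through.** The plan states no figure on this point. The check compares the texts and then counts the procedures that depend on the class.

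**Classification.** Take a woman with at least 12 months of amenorrhea, no alternative medical cause, no hormonal contraception, no HRT, and a Screening FSH below the postmenopausal range.

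1. WOCBP list: she is WOCBP until she becomes postmenopausal, and a high FSH is required to confirm that. Hers is not high, so confirmation fails and she stays WOCBP.
2. WONCBP category 2: she meets the 12-month definition and FSH is optional, so she can be classed WONCBP.
3. No other text breaks the tie. Table 1 footnote i and Section 4.1.1 ensure that a result normally exists, but neither says how to act on a low one. The unclear-fertility sentence assigns no class. Criterion 6B points to Appendix 13 without saying which list governs.

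A woman with no FSH result is a different case. There, a scheduled test has been omitted.

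**Scheduled pregnancy tests that depend on the class.** The inputs are the pregnancy-test rows of Tables 1 and 2. On treatment means excluding Screening, Week 1 and End of Study, so three tests are subtracted.

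| Path | Blinded period | Open label | End of Study | Total | On treatment |
|---|---|---|---|---|---|
| Full 24 weeks blinded | 7 (Screening, Weeks 1, 5, 9, 13, 17, 21) | 8 (Weeks 25 to 53) | 1 | 16 | 16 − 3 = 13 |
| Open-label entry at Week 13 (Table 2 footnote p) | 4 (Screening, Weeks 1, 5, 9) | 8 | 1 | 13 | 13 − 3 = 10 |

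**With one year of long-term extension (LTE), an assumption.** Table 3 has visits every 28 days in the first year, and SAP Table 12 places Months 1 to 12 at Days 393 to 701. That gives (701 − 393)/28 + 1 = 12 further tests. Week 53 is shared with the start of the LTE and is not counted again, and Month 12 is taken as the last-dose visit.

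- Full blinded period: 16 + 12 = 28 tests, of which 13 + 12 = 25 on treatment.
- Week 13 entry: 13 + 12 = 25 tests, of which 10 + 12 = 22 on treatment.

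Early Termination tests, unscheduled tests and any extra serum test needed for the 3-day pre-dose window in criterion 6B are not counted. The Screening test may be done before the FSH result is known, so it may not be lost in practice.

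**The case against.** The strongest reply is that the two bullets can be followed together. Optional wording does not forbid the test, so a site that tests every such woman complies with both. The schedule already applies the stricter rule: the sample is taken at Screening, its stated purpose is confirmation, and screening results decide eligibility. On this view the problem arises only if a site runs the confirmatory test, gets a result that does not confirm menopause, and disregards it. A low FSH also raises doubt about whether another medical cause has been excluded.

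Much of this stands. The schedule shows that the mandatory rule is the intended one, and it narrows the problem to the below-range result. It does not remove the contradiction, because complying with the sampling requirement still leaves the class of that woman undecided, and no sentence gives one list precedence.

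Two further points are fair. The LTE counts depend on qualifying for the extension, and they are not upper limits because early entrants may stay longer than a year. Adult screening may also have been over or nearly over by Amendment 05 (15 May 2024), since SAP version 3, written for the adult analysis, is dated 18 March 2024. The documents do not say that adult enrollment had closed, so that is only an inference.

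**Conclusion.** The inconsistency is real, and its severity is minor. The affected group is likely to be small and cannot be sized from the documents. For each affected woman, the WONCBP class removes 16 scheduled pregnancy tests (13 on treatment), or 13 (10 on treatment) with Week 13 entry. With an assumed full LTE year the figures are 28 (25) and 25 (22). The class also removes the contraception requirement. These are counts of procedures, not an estimate of pregnancy risk.

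Her eligibility does not turn on the point alone, because criterion 6B also admits a WOCBP who uses contraception. The exclusion of pregnant women and the pregnancy stopping rule apply whatever her class. Efficacy, alpha and power are not affected.

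**What to change.** In Appendix 13.1, WONCBP category 2, replace *may be used* with *must be used*, and add two sentences:

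*A missing or non-analyzable Screening FSH is to be repeated before randomization. A woman whose FSH does not confirm menopause is managed as WOCBP.*

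The word change and the second sentence settle the contradiction. The first sentence goes beyond the core defect. It prevents a lost sample from imposing contraception on a clearly postmenopausal woman.

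The cost is an occasional repeat FSH, since the sample is already scheduled. Repeats are familiar in the protocol. Section 7.2, which sets a minimum gap of 7 days, says "Where the clinical significance of an abnormal screening test result (lab or any other tests) is considered uncertain, the test may be repeated once". Section 7.9.6 says "Screening laboratory safety tests may be repeated upon discussion with the Sponsor/Medical Monitor". Neither expressly covers a missing FSH, which is why the added sentence is needed. A 7-day repeat fits the 28-day screening period (up to 31 days under Table 1 footnote a). The change needs the usual amendment approvals and can travel with the next amendment.
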